If subjects are unable or unwilling to attend these visits, they will be contacted by phone or email, and an attempt will be made to obtain measures in this manner.

F. Objectives

Primary: The primary goal of the current study is to investigate the effects of repetitive transcranial magnetic stimulation (rTMS) targeting the left DLPFC on cocaine craving. The co-primary goal is to investigate rTMS effect on cocaine consumption.

Secondary: Our secondary goals are to evaluate rTMS effects on: (1) mood; (2) cognitive functions.

Exploratory: Our exploratory goals are evaluating rTMS effects on: (1) BOLD response in DLPFC during tasks known to activate this area; (2) resting state functional connectivity between the DLPFC and nodes of the executive control networks.

Outcomes measures: Our primary outcomes will be: (1) change in craving score as measured by the CCQ from pre- to post treatment [baseline and after rTMS treatment: 2 weeks, 3 months, 6 months]; (2) changes in cocaine consumption as measured by TLFB self-reports and urine drug screen from pre- to post treatment [baseline and after rTMS treatment: 2 weeks, 3 months, 6 months]. Our secondary outcomes are: Changes in the scores on the 90

Symptoms Questionnaire (SCL-90) from pre- to post treatment [baseline and after rTMS treatment: 2 weeks, 3 months, 6 months]; (2) changes in the scores of the Montgomery-Asberg Depression Scale (MADRS) from pre- to post treatment [baseline and after rTMS treatment: 2 weeks, 3 months, 6 months]; (3) changes in the scores on the Hamilton Anxiety Rating Scale (HARS); (4) changes in the scores on the frontal assessment battery (FAB), and on the Flanker task from pre- to post treatment [baseline and after rTMS treatment: 2 weeks, 3 months, 6 months];

(5) changes in the scores of the Iowa Gambling Task from pre- to post treatment [baseline and after rTMS treatment: 2 weeks, 3 months, 6 months];

In addition, in order to investigate DLPFC engagement by TMS, the following exploratory outcomes will be analyzed: (1) DLPFC BOLD signal change in response to cocaine-related stimuli from baseline to each time point [baseline and after rTMS treatment: 2 weeks, 3 months]. (2) Change in resting state functional connectivity, from baseline to each time point (z-score) [baseline and after rTMS treatment: 2 weeks, 3 months].

1. Aims

Primary aim:

To determine the effects of rTMS on cocaine craving and consumption in patients with CUD.

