- Changes in CCQ score between the active rTMS and sham group, and from pre- to post treatment [baseline and after rTMS treatment: 2 weeks, 3 months, 6 months];
- Percent of negative urine samples between the active rTMS and sham group, and from pre- to post treatment [baseline and after rTMS treatment: 2 weeks, 3 months, 6 months].

Secondary aims:

- Changes in the scores on the 90 Symptoms Questionnaire (SCL-90) from pre- to post treatment [baseline and after rTMS treatment: 2 weeks, 3 months, 6 months];
- Changes in the scores of the Montgomery-Asberg Depression Scale (MADRS) from pre- to post treatment [baseline and after rTMS treatment: 2 weeks, 3 months, 6 months];
- Changes in the scores on the Hamilton Anxiety Rating Scale (HARS);

- Changes in the scores on the frontal assessment battery (FAB), and on the Flanker task from pre- to post treatment [baseline and after rTMS treatment: 2 weeks, 3 months, 6 months];
- Changes in the scores of the Iowa Gambling Task from pre- to post treatment [baseline and after rTMS treatment: 2 weeks, 3 months, 6 months];

Exploratory aims:

- DLPFC BOLD signal change in response to cocaine-related cues from baseline to each time point, and between the active and sham group;
- Changes in resting state functional connnectivity between the DLPFC and other nodes of the executive control network (ECN), from baseline to each time point, and between the active and sham group.

Statistical Analysis

Behavioral measures on each of the cognitive tasks as well as questionnaire data from each of the experimental conditions will be compared both within and between experimental groups using mixed, repeated-measures ANOVA, and linear mixed models. When assessing the statistical results from the behavioral and questionnaire data, a standard α -level of 0.05 will be used. Alpha-levels for multiple comparison follow-up tests will be corrected using an appropriate method (e.g., Bonferroni, Tukey, Scheffe).

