The imaging data will be pre-processed and analyzed with MatLab. All functional images will be directly registered upon high resolution MPRAGE anatomical scans obtained during the same imaging session. Location and intensity of activations from individual and/or grouped data will be translated into 3D stereotaxic coordinates. Functional images of activation-induced BOLD signal changes will be determined using cross correlation or multiple regression analyses. Differences in structural and functional measures between active rTMS and sham participants will be assessed using between group comparisons (e.g., independent samples t-tests). Correlation and multiple regression approaches will be used to test for an association between clinical assessment measures and task-specific neural

measures (e.g., correlation between cocaine craving scores and neural activation in the striatum).

Real vs Sham rTMS Power Analysis. Because no sham-controlled studies have been performed assessing the chronic effects of rTMS administration on behavioral or neurophysiological measures in patients with CUD, anticipating an effect size is difficult. However, open label studies have shown substantial behavioral changes in clinical populations and could have similar effects in reducing cocaine use. In order to capture a reliable effect while not committing a type II error, a medium-large effect size (Cohen's d = 0.65) will be used to calculate the necessary participants to compare real and sham iTBS treatments. Approximately 30 participants per group will be required to detect significant differences between these two independent groups at a nominal α level of 0.05 in a one-tailed t-test assuming a medium-large effect size. We anticipate approximately 80-85% retention rate at visit 24, based on previous studies conducted in similar patient populations by our group. Therefore, 80 participants will be recruited at baseline, 40 for real and 40 for sham iTBS, to acquire the necessary 30 participants in each group for analysis.

G. Data Management and Safety measures

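### Craving and consumption are both primary, but the plan states no success rule and no error control across the two; if either may succeed at 0.05, family-wise error can approach 10%

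*Combined protocol and SAP*

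**What the plan says.** Section F (Objectives) names craving as the primary goal and adds: "The co-primary goal is to investigate rTMS effect on cocaine consumption". Its outcomes paragraph lists two primary outcomes. The first is "change in craving score as measured by the CCQ from pre- to post treatment [baseline and after rTMS treatment: 2 weeks, 3 months" and 6 months. The second is "changes in cocaine consumption as measured by TLFB self-reports and urine drug screen", on the same schedule. Section 1 (Aims) joins them in one primary aim: "To determine the effects of rTMS on cocaine craving and consumption in patients with CUD". Under that aim, consumption is represented only by "Percent of negative urine samples between the active rTMS and sham group, and from pre- to post treatment"; the TLFB does not appear.

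The Statistical Analysis section plans repeated-measures ANOVA and linear mixed models. It sets alpha at 0.05 with the words "When assessing the statistical results from the behavioral and questionnaire data", and then says "Alpha-levels for multiple comparison follow-up tests will be corrected using an appropriate method (e.g., Bonferroni, Tukey, Scheffe"). The power paragraph sizes a single comparison at Cohen's d = 0.65, "in a one-tailed t-test assuming a medium-large effect size". It gives about 30 per group for analysis and 40 per group recruited, and ties the effect size to neither outcome.

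**The concern.** Correction of follow-up tests can deal with several time points within one outcome. It does not deal with having two outcomes, each of which could support the headline claim. The plan gives no testing order, no division of alpha, and no statement that one outcome is enough or that both are needed. It names neither the time point nor the overall test that carries the primary claim, and its two descriptions of consumption differ.

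What is at stake depends on the rule eventually applied. If a positive result on either outcome counts as success, the chance of a false claim can exceed 5%. If both are needed, that chance is controlled, but the trial has less power than its sample-size paragraph suggests. With the rule unwritten, it could be settled after the results are known.

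**Working it through.** **Inputs from the documents.** Two primary outcomes; three post-baseline time points; alpha 0.05; d = 0.65; one-tailed t-test; 30 per arm for analysis; 40 per arm recruited; 80-85% retention at visit 24.

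**Assumptions.** The correlation between the two test statistics (0 to 0.8) and between time points (0 to 0.8), since the documents give neither. A level of 0.05 for the urine result, since the stated level refers to behavioural and questionnaire data. Sidedness of the analysis, since only the sample-size test has one. Power of 80%, which the plan does not state.

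**1. The plan's own figure.** n per arm = 2(z₀.₉₅ + z₀.₈₀)²/d² = 2(1.645 + 0.842)²/0.65² ≈ 29.3, so 30. The noncentral t gives 80.0% power at 30 per arm. The stated figure is reproduced for one outcome, one-tailed. A two-sided test would need 38.

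**2. Either outcome is enough, one test each at 0.05.** Under independence the error is 1 − 0.95² = 9.75%. With correlated bivariate normal statistics it is:

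| Outcome correlation | Two-sided | One-tailed |
|---|---|---|
| 0 | 9.75% | 9.75% |
| 0.3 | 9.5% | 9.3% |
| 0.5 | 9.1% | 8.8% |
| 0.8 | 7.8% | 7.5% |

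**3. Either outcome is enough, Bonferroni over three time points within each outcome (0.05/3 per test).** This was simulated with 1,000,000 draws per setting. For outcome correlation 0.5 to 0, two-sided error is about 9.1-9.6% at time correlation 0, 8.2-8.8% at 0.5 and 6.5-6.9% at 0.8. One-tailed error over the same settings is 6.1-9.6%. With both correlations at 0.8 it is about 5.7% two-sided and 5.2% one-tailed. The overall range is about 5.2-9.6%.

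**4. As step 3, but follow-up tests count only after a significant 3-df omnibus test at 0.05 for that outcome.** The plan does not state this gate. Two-sided error is about 3.6-6.7%. For outcome correlation 0-0.5 it is 6.4-6.7% at time correlation 0, 5.5-5.8% at 0.5 and 4.2-4.4% at 0.8. If the omnibus result alone may be claimed for either outcome, error is about 9.2-9.8% for outcome correlation 0-0.5.

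**5. Both outcomes must succeed.** Error is at most 5%. Expected completers per arm at visit 24 are 40 × 0.80 = 32 to 40 × 0.85 = 34. Joint power, one-tailed at 0.05 with d = 0.65 on both outcomes:

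| Per arm | One outcome | Both (correlation 0 to 0.5) |
|---|---|---|
| 30 | 80.0% | 64-69% |
| 32 | 82.3% | 68-72% |
| 34 | 84.3% | 71-75% |
| 40 | 89.2% | 80-82% |

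At zero correlation the first row is 0.800² = 0.64.

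**The case against.** The strongest reply is that co-primary often means both outcomes must succeed, and the single joint aim points the same way. Error is then at most 5% with no alpha split. This stands as a possible reading. The plan, however, attaches the word to a goal and gives no decision rule, and its sample size considers one comparison rather than two jointly. On that reading the cost moves to power.

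A second reply is that follow-up tests normally come after a significant omnibus test. Step 4 shows that such a gate can bring error below 5% even if either outcome is enough. This also stands, although the plan does not state the gate and it does not hold error below 5% in every setting tried.

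A reader might therefore infer that the plan's type I error definitely exceeds 5%. The documents do not support that: the excess depends on the success rule, the gating and correlations that are not given. A reader might also infer that a single time point must become primary and the others be demoted. That is not needed to control error across the two outcomes; one group-by-time test per outcome over all visits would also serve.

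Finally, the power figures are illustrative. They use an unadjusted t-test with the same d on both outcomes, whereas the plan analyses repeated measures. The 30 per arm is also the plan's minimum; its retention figures imply 32-34.

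**Conclusion.** The omission is established from the text: two primary outcomes, no success rule, and no error control between them. Its size is conditional. If either outcome may succeed on one test at 0.05, family-wise error is between 9.75% and about 7.5% for assumed correlations of 0 to 0.8. Correction over time points narrows this to about 5.2-9.6%, and an added omnibus gate can take it below 5%. If both must succeed there is no inflation, but illustrative joint power is 64-69% at 30 per arm and 68-75% at 32-34. Confidence is high in the omission and lower in any single figure. Because the repair is small and the excess depends on how the plan is read, this is rated a cheap improvement.

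**What to change.** Before unblinding, add to the Statistical Analysis section:

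- One active-versus-sham primary test per outcome, at the sponsor's choice: a contrast at a single time point, or one group-by-time test over all visits. State its sidedness.
- One consumption measure, reconciling the outcomes paragraph of section F (TLFB and urine screen) with the primary aim in section 1 (urine only), and the alpha level that applies to it.
- One rule across the two outcomes: (a) Holm at an overall 0.05; (b) a fixed sequence, craving then consumption, each at 0.05; or (c) both must succeed at 0.05 each, with the resulting joint power reported and no extra enrolment.

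The cost is a few sentences, with no new data or participants. The power costs below use the plan's one-tailed test at 30 per arm. Holm lowers power per outcome from 80% to about 76-77% if both effects are d = 0.65 (correlation 0-0.5), or to about 70% if only one is real. The fixed sequence keeps craving at 80%, but consumption can be confirmed only if craving succeeds, a probability of about 64-69%. Option (c) accepts that same joint power as the power of the trial.

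### The exploratory imaging outcomes are changes from baseline, but the only between-arm method named is a t-test without the baseline scan as covariate, which gives up precision at no saving

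*Combined protocol and SAP*

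**What the plan says.** Section F (Objectives, Outcomes measures) lists two exploratory imaging outcomes, each measured at baseline, 2 weeks and 3 months: "DLPFC BOLD signal change in response to cocaine-related stimuli from baseline to each time point" and "Change in resting state functional connectivity, from baseline to each time point (z-score"). The Exploratory aims add the comparison of arms; for the first outcome the aim is "DLPFC BOLD signal change in response to cocaine-related cues from baseline to each time point, and between the active and sham group", and the connectivity aim uses the same form.

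The Statistical Analysis section gives one method for that comparison: differences between active and sham participants "will be assessed using between group comparisons (e.g., independent samples t-tests"). It does not say whether the t-test is applied to change scores or to follow-up values, and it names no baseline covariate.

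Two other methods in that section do not fill the gap:

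- The mixed ANOVA and linear mixed models are introduced for non-imaging data: "Behavioral measures on each of the cognitive tasks as well as questionnaire data from each of the experimental conditions will be compared" by those methods.
- Multiple regression appears twice for imaging. One use is to derive the BOLD signal changes themselves. The other is to relate brain to clinical measures: "Correlation and multiple regression approaches will be used to test for an association between clinical assessment measures and task-specific neural" measures. Neither is the estimate of the treatment effect.

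**The concern.** The baseline scan carries information about each participant's later scans. A t-test on follow-up values discards it. A t-test on change scores subtracts the baseline in full, which over-corrects whenever the correlation is below 1 and the SDs are equal. A regression on the baseline value lets the data set the weight, and for any correlation strictly between 0 and 1 it is more precise than either t-test.

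What is at stake is the width of the confidence intervals on the question the imaging is there to answer, namely whether the stimulation engages the DLPFC. The groups are small, so chance differences at baseline can be sizeable. Leaving the input to the t-test unstated also means that the choice between change and follow-up values could be made after the data are seen.

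**Working it through.** **The plan's own figure.** The power analysis states that "a medium-large effect size (Cohen's d = 0.65) will be used", with a one-tailed t-test at 0.05 and about 30 per group. Power is not stated. Assuming 80%, n = 2 × ((1.645 + 0.842)/0.65)² = 29.3, so 30 per arm; the exact noncentral t calculation also gives 30 (power 80.0%). The figure reproduces. It is not tied to an imaging outcome, and imaging has no sample size of its own.

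**Inputs for the comparison of methods**

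- From the documents: 1:1 allocation, 40 recruited per arm, baseline and two follow-up scans.
- Assumed: equal SD at baseline and follow-up; r = 0.3, 0.5 or 0.7; 32 analysed per arm. The last is 40 × 0.80, the lower end of the 80-85% retention that the plan gives for visit 24. The plan gives no retention at the scan times.

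**Variance of the arm difference, in units of 2σ²/n**

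- Follow-up t-test: 1
- Change-score t-test: 2(1-r)
- Baseline-adjusted: 1-r²

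The ratio of adjusted to change-score is (1-r²)/(2(1-r)) = (1+r)/2, a saving of (1-r)/2. The ratio of adjusted to follow-up is 1-r², a saving of r².

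| r | Change-score | Adjusted | Saving vs change-score | Saving vs follow-up |
|---|---|---|---|---|
| 0.3 | 1.40 | 0.91 | 35% | 9% |
| 0.5 | 1.00 | 0.75 | 25% | 25% |
| 0.7 | 0.60 | 0.51 | 15% | 49% |

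A simulation with 30 per arm and 6000 runs gave variances of 1.37, 0.98 and 0.61 for the change score and 0.92, 0.77 and 0.52 for the adjusted estimate, in line with the formulas.

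**Detectable difference** (32 per arm, two-sided 5%, 80% power, exact t). For the follow-up t-test it is 0.71 SD. The others follow by multiplying by the square root of the variance above; at r = 0.5, for example, 0.71 × √0.75 = 0.62.

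| r | Follow-up t | Change-score t | Adjusted |
|---|---|---|---|
| 0.3 | 0.71 | 0.84 | 0.68 |
| 0.5 | 0.71 | 0.71 | 0.62 |
| 0.7 | 0.71 | 0.55 | 0.51 |

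All are in units of the follow-up SD.

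**On the plan's own basis** (30 per arm, one-sided 0.05, and supposing that 0.65 follow-up SD were also the imaging effect), power for follow-up t / change-score t / adjusted is 80% / 68% / 83% at r = 0.3, 80% / 80% / 89% at r = 0.5, and 80% / 94% / 97% at r = 0.7.

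**The case against.** Several points on the other side stand.

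- **The t-test is only an example.** An adjusted comparison is not excluded. A reader might infer that the plan commits itself to an unadjusted test; it does not. Still, the one method named is the less efficient one, so the model needs to be stated.
- **The baseline scan is probably not ignored.** The outcomes are defined as change, and a follow-up-only t-test would not analyse them as defined. On the change-score reading the baseline is used by subtraction, and the saving from adjustment shrinks as r rises.
- **The gain is not large everywhere.** Setting the adjusted model against the worse t-test at each r (0.84 to 0.68 at r = 0.3, then 0.71 to 0.51 at r = 0.7) would suggest that it is. Against the better t-test at those values it is 0.71 to 0.68 and 0.55 to 0.51.
- **No bias is involved.** A reader might infer that chance baseline differences invalidate the comparison. Under randomisation they add variance only.
- **The contrast with the behavioural data is weak.** A reader might infer that those outcomes are better protected because mixed models are named for them. The plan names no baseline covariate there either, and with two time points and complete data the group-by-time test of a mixed ANOVA is the same as a t-test on change scores.
- **The outcomes are exploratory.** They drive neither the sample size nor the primary conclusion.

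What remains is that, within the stated model, adjustment gains some precision at every r strictly between 0 and 1, from scans already planned.

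**Conclusion.** The point holds as one of efficiency and specification. On the change-score reading, adjusting for the baseline scan lowers the variance of the arm difference by 15% to 35% for r between 0.7 and 0.3; on the follow-up reading, by 9% to 49% for r between 0.3 and 0.7. The variance ratios rest on equal SDs and on r, which the documents do not give, but not on the number scanned. The detectable differences rest in addition on the assumed 32 per arm.

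The documents do not support reading this as a flaw in the validity of the imaging comparison, or as bearing on the craving and consumption analyses. It is worth correcting because it costs nothing.

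**What to change.** In the imaging paragraph of the Statistical Analysis section, replace the t-test for DLPFC BOLD response and for DLPFC connectivity with the executive control network by one of the following:

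- an ANCOVA at each time point, with the follow-up value as response and with arm and the baseline scan value as covariates; or
- a linear mixed model over 2 weeks and 3 months with arm, time, arm × time and the baseline scan value.

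Report the arm difference at 2 weeks and at 3 months with 95% confidence intervals. A site term is optional: recruitment is in two cities, but the Research MR section describes a single scanner.

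The cost is a change of wording, made before the imaging data are analysed. No scan, visit or participant is added.

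### The 30 per group is sized on a one-tailed t-test that the analysis section does not carry forward, so it is unsupported for the planned analysis, though not shown to be too small

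*Combined protocol and SAP*

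**What the plan says.** The paragraph headed Real vs Sham rTMS Power Analysis (section F, Statistical Analysis) takes d = 0.65 and alpha 0.05 and concludes: "Approximately 30 participants per group will be required to detect significant differences between these two independent groups". The test assumed is stated directly: "in a one-tailed t-test assuming a medium-large effect size". No power figure is given. On dropout it says "We anticipate approximately 80-85% retention rate at visit 24", and it recruits 40 per group "to acquire the necessary 30 participants in each group for analysis". Its support for expecting benefit is that "open label studies have shown substantial behavioral changes in clinical populations"; it also says that an effect size is hard to anticipate because no sham-controlled studies exist.

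The opening paragraph of Statistical Analysis describes a different analysis. Cognitive-task and questionnaire data "will be compared both within and between experimental groups using mixed, repeated-measures ANOVA, and linear mixed models", and "a standard α -level of 0.05 will be used". Direction is not mentioned. The first primary outcome, "change in craving score as measured by the CCQ from pre- to post treatment", is questionnaire data and falls under this sentence. It is measured at baseline, 2 weeks, 3 months and 6 months.

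**The concern.** The test used to size the trial is not a test that the plan says it will run. The term one-tailed appears only in the power paragraph. The ANOVA F-test is non-directional, and for the mixed models the plan names neither a contrast nor a direction. The only t-tests mentioned for analysis concern the imaging measures, and no sidedness is given for them either. Open-label results explain why benefit is expected, but the plan offers no argument for a one-sided test.

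Two things are at stake. A reader who takes the sizing statement at face value would credit the trial with more power than a two-sided comparison of the same kind has. And with direction and contrast both open, sidedness could be settled after the data are seen.

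**Working it through.** **Inputs.** From the power paragraph: d = 0.65, alpha 0.05, one-tailed two-sample t-test, 30 per group analysed, 40 per group recruited, 80-85% retention at visit 24. From the Study Overview: 1:1 allocation. Retention implies 40 × 0.80 = 32 to 40 × 0.85 = 34 per group at that visit.

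**Step 1: reproduce the plan's figure.** Power from the noncentral t, with df = 2n − 2 and noncentrality 0.65 × √(n/2). At n = 30, df = 58 and the noncentrality is 0.65 × √15 = 2.517. The one-sided critical value is 1.672, which gives 80.0% power. At n = 29 power is 78.8%, so 30 is the smallest n that reaches 80% one-sided. One-sided targets of 70%, 85% and 90% need 23, 35 and 42 per group. An 80% target is therefore the natural reading, but it is inferred.

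**Step 2: same comparison, two-sided.** At n = 30 the critical value becomes 2.002.

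| n per group | One-sided power | Two-sided power |
|---|---|---|
| 30 | 80.0% | 69.7% |
| 32 | 82.3% | 72.6% |
| 34 | 84.3% | 75.2% |
| 40 | 89.2% | 81.9% |

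Two-sided power is 79.9% at 38 per group and 80.9% at 39, so 80% needs 39. At 30 per group, the d detectable with 80% two-sided power is 0.74.

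**Step 3: link to ANOVA.** A two-group F-test on 1 and 2n − 2 df has noncentrality 0.65² × n/2. At n = 30 this is 0.4225 × 15 = 6.34 = 2.517², and power is again 69.7%. A pre-post group-by-time F-test with two visits is equivalent to a two-sided t-test on change scores.

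**Step 4: how far the planned longitudinal models could differ.** The documents give no correlation, no contrast and no scale for d, so the following are assumptions: four visits, compound symmetry with correlation ρ, and a constant effect δ at the three post-baseline visits. All tests are non-directional or two-sided at 0.05, with n = 30.

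- *Omnibus group-by-time F*, 3 and 3(2n − 2) = 174 df, noncentrality (n/2) × 0.75δ²/(1 − ρ). The 0.75 is the sum of squared deviations of the pattern (0, 1, 1, 1) from its mean.
- *One-degree-of-freedom contrast*, mean of the post-baseline visits minus baseline, df = 2n − 2, noncentrality δ/√[(2/n)(1 − ρ)(4/3)].

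If d is on the raw-score SD, δ = 0.65. If d is on the change-score SD, δ = 0.65 × √[2(1 − ρ)] and ρ cancels: the noncentralities are 0.75 × 30 × 0.4225 = 9.51 for the F-test and 3.08 for the contrast.

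| Test at 30 per group | Change-score d, any ρ | Raw d, ρ = 0.3 | Raw d, ρ = 0.5 | Raw d, ρ = 0.7 |
|---|---|---|---|---|
| Omnibus F, 3 df | 73% | 56% | 73% | 93% |
| 1-df contrast, two-sided | 86% | 73% | 86% | 97% |

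The range is about 56-97%, on both sides of the 70% two-sample figure and of 80%.

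**The case against.** The strongest reply is that the planned analysis is not a two-sample comparison, so 70% is not its power. This stands. Under the assumptions in step 4, a two-sided one-degree-of-freedom contrast exceeds 80% at 30 per group in several cases, and even the less efficient omnibus F-test reaches 93% in one. The plan does not specify either contrast, so it cannot rely on such a gain, but neither can a critic rule it out.

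Second, the analysis section is silent on direction. Its alpha of 0.05 is not labelled two-sided, and a mixed-model contrast can be tested one-sided. This also stands: two-sided is the conventional reading, not a quoted statement. The clear mismatch is with the ANOVA F-test, one of the two named methods.

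Third, no power target is stated, so no target is missed. That is correct, but the loss of about 10 points at 30 per group between one-sided and two-sided tests does not depend on a target.

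Fourth, 40 are recruited, outcomes are also taken at 2 weeks and 3 months, and mixed models can use partial data. This is fair: the 32-34 applies to visit 24, the only retention figure given. If all 40 contribute, two-sided power is 81.9% on the two-sample basis.

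A reader might go further and infer that the trial is too small and needs 39 analysed per group, hence 39/0.85 to 39/0.80, or 46-49 recruited per group and 92-98 in all. The documents do not support that. It would require the primary test to be a single-visit two-sided two-sample comparison with an 80% target, and the plan states neither.

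**Conclusion.** The concern holds as a mismatch between the sizing basis and the analysis. The 30 per group rests on a one-sided test that the analysis section does not contain and the plan does not justify. Like for like, moving to two-sided lowers power for d = 0.65 from 80% to 70% at 30 per group, and from 82-84% to 73-75% at 32-34. The chance of missing that effect rises from 20% to 30%, and from 16-18% to 25-27%.

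These are two-sample figures for a continuous outcome such as the CCQ. They do not size the other primary measure, percent of negative urine samples. For the planned longitudinal models the 30 is unverified: power could be well below or well above the two-sample figure, and the plan gives no basis for choosing. The one-sided match to 80%, the sidedness ratio and the detectable d are firm. The 56-97% range is illustrative and depends on the assumptions listed with it. This should be fixed, but it does not invalidate the trial.

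**What to change.** Keep N = 80 and keep craving and consumption as co-primary.

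- **Statistical Analysis, opening paragraph.** Name the primary between-group contrast for the CCQ (which visit or visits, and change or raw score) and state that it is tested two-sided at alpha 0.05.
- **Power-analysis paragraph.** Replace the one-tailed basis and the description of 30 per group as necessary. One option is a statement labelled as a two-sample approximation for a continuous outcome such as the CCQ, and not for percent negative urines: two-sided at 0.05, 73-75% power for d = 0.65 with 32-34 per group at the final visit, 70% at 30 and 82% at 40; detectable d with 80% power at 30 per group, 0.74. The better option is power for the named contrast, with the correlation assumptions and the scale of d stated. Without the label or the named contrast, the rewording would only swap one t-test mismatch for another.
- **If a one-sided test is intended.** Pre-specify and justify it in the analysis section for a named one-degree-of-freedom between-group contrast, since the ANOVA F-test cannot deliver it. The 30 may then stay.

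The cost is a few sentences and no added patients. On the two-sample option the stated power becomes less favourable; the change discloses the lower figure and does not raise it. The one-sided route needs a written justification that readers may question.
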